11 OTHER ANALYSES

Not applicable.

This document cannot be used to support any marketing authorization application and any extensions or variations thereof.

PUBLIC COPY

12 REFERENCES

This document cannot be used to support any marketing authorization application and any extensions or variations thereof.
PUBLIC COPY

13 APPENDICES**13.1 PCS criteria****13.1.1 Hematology, clinical chemistry and endocrinology parameters****Table 13-1: Hematology, clinical chemistry, and endocrinology parameter abnormality criteria**

Parameter	Age Range	UNIT	Abnormality Criteria
Hematology			
Hematocrit	≥2y - <18y	%	≤29 ≥47
	≥18y		≤85% of LLN ≥115% of ULN
Hemoglobin	≥2y - <18y	g/L	≤95 ≥160
	≥18y		≤85% of LLN ≥115% of ULN
WBC/Leukocytes	<12y	G/L	<3.5 ≥15.0
	≥12y		<3.0 ≥12.0
Neutrophils Absolute	>1m	G/L	<1.5
Lymphocytes	≥6m - <6y	%	≤22.0
	≥6y - <18y		≤12.0 ≥80.0
	≥18y		≤10.0 ≥80.0
Basophils	>1m	%	≥3.0
Eosinophils	>1m	%	≥10.0
Monocytes	>1m	%	≥20.0
Platelets	>1m	G/L	≤100 ≥600
RBC/Erythrocytes	≥2y	T/L	<3.5
Biochemistry			
AST (SGOT)	<14y	U/L	>180

Table 13-1: Hematology, clinical chemistry, and endocrinology parameter abnormality criteria

Parameter	Age Range	UNIT	Abnormality Criteria
	≥14y		>144
ALT (SGPT)	1y - <18y	U/L	>90
	≥18y		>123
Alkaline Phosphatase	<4y	U/L	>690
	≥4y - <10y		>834
	≥10y - <18y		>1174
	≥18y		>432 (F) >933 (M)
Total Bilirubin	>1m	umol/L	≥25.656
Total Protein	≥1y	g/L	<43 >100
Blood Urea Nitrogen (BUN)	≥1y	mmol/L	>10.71
Creatinine	1y - <10y	umol/L	>79.56
	≥10y - <16y		>123.76
	≥16y		>141.44
Creatinine Clearance ^a	All	mL/s	<1.169
Calcium	1y - <18y	mmol/L	<1.85 >2.925
	≥18y		≤1.975 ≥2.775
Potassium	≥1y	mmol/L	<3.0 >5.8
Sodium	>1m	mmol/L	≤130 ≥150
Glucose	>1m	mmol/L	<2.775 ≥9.99
Thyroxine (T4)	≥1y	nmol/L	≤48.9098 ≥173.7585

m=month; y=year.

ALT=alanine aminotransferase; AST=aspartate aminotransferase; BUN=blood urea nitrogen; CrCl=creatinine clearance; dL=deciliter; eCRF=electronic case report form; L=liter; LLN=lower limit of normal; μg =microgram; m=month (defined as 30 days); mg=milligram; PCS=possibly clinically significant; PCST=possibly clinically significant treatment-emergent; U=unit; ULN=upper limit of normal; y=years (defined as 365.25 days)

^aSchwartz equation (study participants <12): CrCl ml/min=[Height (cm) * 0.55] / serum creatinine (mg/dL)

Cockcroft equation (study participants ≥ 12): Male: CrCl ml/min=[(140-age) x body weight (kg)] / (72 x serum creatinine [mg/dL]); Female: CrCl ml/min=[(140-age) x body weight (kg)] / (72 x serum creatinine [mg/dL]) x 0.85

Note: Age is collected on the eCRF at each visit and will be used for derivations of PCS assessments.

Note: Creatinine Clearance is converted from mL/min to mL/s by dividing by 60.

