8.2.6 Adverse events of special interest

An AE of special interest is any AE that a regulatory authority has mandated be reported on an expedited basis, regardless of the seriousness, expectedness, or relatedness of the AE to the administration of a UCB product/compound.

For BRV, the following events require immediate reporting (within 24 hours regardless of seriousness) to UCB:

- Autoimmune nephritis
- Nephritis

- Nephritis allergic
- Tubulointerstitial nephritis
- Tubulointerstitial nephritis and uveitis syndrome
- Potential Hy's Law, defined as $\geq 3 \times \text{ULN}$ ALT or aspartate aminotransferase with coexisting $\geq 2 \times \text{ULN}$ total bilirubin in the absence of $\geq 2 \times \text{ULN}$ alkaline phosphatase, with no alternative explanation for the biochemical abnormality, must ALWAYS be reported to UCB as an AE of special interest (ie, without waiting for any additional etiologic investigations to have been concluded). Follow-up information should then be reported if an alternative etiology is identified during investigation and monitoring of the participants.

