3.4 Possibly clinically significant values

PCST values are any laboratory measurements, vital signs or ECG parameters which meet the criteria defined in [Section 13.1](#) which occur any time after the first dose of BRV has been taken in EP0132. PCS criteria are based on Food and Drug Association Division of Neuropharmacological Drug Products guidelines with some UCB-defined additions. Assessment of whether a measurement fulfils age-dependent PCS criteria will be performed using the age of the participant in years at the visit. Measurements that meet PCS criteria and are treatment-emergent will be considered PCST regardless of whether or not they met the criteria for PCS previously.

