Summaries and listings of study participants with PCST values for laboratory variables will include all planned and unplanned variables from central and local laboratories. In the unlikely event that there are both central and local laboratory measurements on the same calendar date, preference will be given to the central laboratory result. Summaries of PCST values for urinalysis will only include data from central laboratories.

A listing of additional laboratory tests will be provided including urine and serum pregnancy tests and urine drug screen tests (performed as part of the PDILI assessments described in [Section 10.3.2](#)).

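### The creatinine clearance equation changes at age 12 under a single cut-off, so a participant who turns 12 on study can gain or lose a flag with height, weight and creatinine unchanged

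*SAP*

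**What the plan says.** The creatinine clearance row of SAP Table 13-1 (Section 13.1.1) has a single limit, below 1.169 mL/s, for all ages. Footnote a gives two ways of obtaining the value:

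- Under 12 years, the Schwartz equation: 0.55 times height in cm, divided by serum creatinine in mg/dL. Weight and sex do not enter.
- From 12 years, the Cockcroft equation, which uses weight, age and sex but not height. For girls it reads "Female: CrCl ml/min=[(140-age) x body weight (kg)] / (72 x serum creatinine [mg/dL]) x 0.85". For boys it begins "Cockcroft equation (study participants ≥ 12): Male: CrCl ml/min=[(140-age) x body weight (kg" and has the same denominator without the 0.85.

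The result is put on the scale of the limit by a stated conversion: "Creatinine Clearance is converted from mL/min to mL/s by dividing by 60".

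Two statements settle which age applies. The note under the table says "Age is collected on the eCRF at each visit and will be used for derivations of PCS assessments". SAP Section 3.4 says "Assessment of whether a measurement fulfils age-dependent PCS criteria will be performed using the age of the participant in years at the visit". Section 3.4 also removes any requirement for a change from an earlier value: "Measurements that meet PCS criteria and are treatment-emergent will be considered PCST regardless of whether or not they met the criteria for PCS previously".

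Serum creatinine has its own row in the same table, with limits of >79.56 umol/L (1 to <10 years), >123.76 umol/L (10 to <16 years) and >141.44 umol/L (16 years and over).

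**The concern.** In most age-banded rows of Table 13-1 a birthday changes the limit applied to one measurement. Here the limit stays the same and the way the measurement is calculated changes. One equation scales with height and the other with weight, so they agree at age 12 only at one weight for a given height and sex. A participant who turns 12 during a study of two years or more is on one scale at one visit and on the other at the next.

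The SAP deals with this kind of problem elsewhere. For body weight (Section 13.1.3), age at the EP0132 Entry Visit fixes the method, and participants who reach 17 stay in the younger category. For EpiTrack Junior (Section 3.13.10), the age correction is fixed at N01269 Baseline, or at age 6 for those younger than that. For PedsQL (Section 3.13.11), change is not calculated between the toddler version and later versions. Creatinine clearance has no such rule.

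At stake is the reading of the renal rows in the treatment-emergent PCS (PCST) tables. In a single-arm study no control group would show that some flags arise from the equation alone.

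**Working it through.** **Inputs.** The equations, the division by 60 and the limits come from Table 13-1 and its notes. Heights, weights and creatinine values are illustrative assumptions. The factor 88.4 (mg/dL to umol/L) is not stated in the SAP, but it turns the three creatinine limits into 0.90, 1.40 and 1.60 mg/dL.

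**The cut-off.** 1.169 x 60 = 70.14 mL/min. The SAP gives no source value in mL/min. 70/60 = 1.167, and 70 x 0.0167 = 1.169. The difference does not affect what follows.

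**Ratio of the two equations at age 12.** With W in kg and H in cm, creatinine cancels:

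- Boys: [(140 - 12) x W / 72] / (0.55 x H) = 3.232 x W/H
- Girls: 0.85 x 3.232 x W/H = 2.747 x W/H

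At 150 cm the switch is neutral at 150/3.232 = 46.4 kg (boy) or 150/2.747 = 54.6 kg (girl). Below that weight clearance drops at 12; above it, clearance rises.

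**A flag gained: girl, 145 cm, 35 kg, 0.8 mg/dL (70.7 umol/L).**

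- Under 12: 0.55 x 145 / 0.8 = 99.7 mL/min = 1.66 mL/s, not PCS.
- At 12: (128 x 35) / (72 x 0.8) x 0.85 = 66.1 mL/min = 1.10 mL/s, PCS.
- The fall is 1 - 66.1/99.7 = 34%, from age alone.

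**A flag lost: boy, 155 cm, 75 kg, 1.3 mg/dL (114.9 umol/L).**

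- Under 12: 0.55 x 155 / 1.3 = 65.6 mL/min = 1.09 mL/s, PCS.
- At 12: (128 x 75) / (72 x 1.3) = 102.6 mL/min = 1.71 mL/s, not PCS.

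**Creatinine above which clearance is flagged.** This is 0.55 x H / 70.14 by height, or 128 x W (x 0.85 if female) / (72 x 70.14) by weight, each x 88.4.

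| Participant at 12 | By height (umol/L) | By weight (umol/L) |
|---|---|---|
| Girl, 140 cm, 30 kg | 97.0 | 57.1 |
| Girl, 145 cm, 35 kg | 100.5 | 66.7 |
| Boy, 145 cm, 35 kg | 100.5 | 78.4 |
| Girl, 155 cm, 75 kg | 107.4 | 142.8 |
| Boy, 155 cm, 75 kg | 107.4 | 168.0 |

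The serum creatinine limit at this age is 123.76 umol/L. In the first three rows, values between the two columns gain a clearance flag at 12 while creatinine itself is not PCS.

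**Heavier adolescents.** For boys of 90 kg, the range flagged by the height equation but missed by both existing rows is:

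- 14 years, 165 cm: height equation above 1.29 mg/dL, Cockcroft above 2.25, creatinine row above 1.40. Missed: about 1.29 to 1.40.
- 16 years, 170 cm: height equation above 1.33 mg/dL, Cockcroft above 2.21, creatinine row above 1.60. Missed: about 1.33 to 1.60.

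**The case against.** The strongest reply is that little depends on this row.

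- Creatinine clearance is not among the laboratory tests in Protocol Section 10.2, and SAP Section 10.3.1 limits the ordinary laboratory summaries to protocol-planned variables. A step at age 12 should therefore not appear in the change-from-Baseline tables. This stands. The PCST outputs are broader: "Summaries and listings of study participants with PCST values for laboratory variables will include all planned and unplanned variables from central and local laboratories". Table 13-1 has a clearance row for that purpose, so the flags would be reported there.
- No primary or secondary endpoint uses the flag, and no testing is planned. This stands.
- The renal adverse events of special interest in Protocol Section 8.2.6, such as "Tubulointerstitial nephritis and uveitis syndrome", are reported as events and do not depend on a clearance flag. This stands, so the list does not raise the importance of the point.
- The illustration depends on the creatinine chosen. At 0.7 mg/dL the same girl has 75.6 mL/min at 12 and is not flagged. This stands as a limit on frequency; the ratio itself does not depend on creatinine.

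A reader might infer three stronger points that the documents do not support.

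- That heavy adolescents escape detection. The serum creatinine row has no weight term and flags them above 123.76 or 141.44 umol/L, so the missed range is narrow.
- That light adolescents are flagged at normal creatinine. The documents give no paediatric reference range, and PCS limits are not one.
- That the height equation ought to apply up to 18. Nothing in the documents sets that boundary.

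**Conclusion.** The point holds as a defect in a derivation rule. With one limit, two equations and age taken at each visit, turning 12 can by itself create or remove a PCST flag for creatinine clearance. For a given build the step is a fixed proportion: 3.232 x W/H for boys and 2.747 x W/H for girls. It is down for light children and up for heavy ones, and the creatinine row cannot cancel a clearance flag so created.

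The consequence is modest and confined to descriptive PCST tables and listings. How many of the approximately 140 expected participants would be affected cannot be estimated, because the documents give no distribution of age, body size or creatinine. The conclusion rests on reading the footnote's age limits as age at the visit, which Section 3.4 and the table note support. The individual examples rest on assumed body sizes and creatinine values.

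**What to change.** In footnote a of Table 13-1, state that the equation is chosen once per participant, by age at N01269 Baseline (or at the EP0132 Entry Visit), and kept for all EP0132 PCST assessments. Section 13.1.3 already takes this approach for body weight. Under this rule the girl in the example stays at 99.7 mL/min and is not flagged.

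Optionally, for participants aged 12 to <18 who are flagged on clearance but not on serum creatinine, add a listing of clearance by the height-based equation. This would also help with participants already on the weight-based equation at entry, whom the main change leaves as they are.

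The cost is one sentence and one derivation change. Protocol Section 8.1.2 already provides for height and weight at the MEV, FEV, YEV, EDV and FV. The downsides are a small departure from the sponsor's standard PCS derivation, and that a participant who crosses 12 keeps the height-based equation at older ages. If clearance was derived in N01269, consistency with that derivation should be checked.

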13.1.2 Urinalysis parameters

Urinalysis parameters assessed in this study and their possible values are specified in [Table 13-2](#).

Table 13-2: Urinalysis parameters and possible values

PARAMETER	Possible Values
Bilirubin	NEGATIVE, TRACE, 1+, 2+, 3+
Blood	NEGATIVE, TRACE, 1+, 2+, 3+
Glucose	NEGATIVE, TRACE, 1+, 2+, 3+
Ketones	NEGATIVE, TRACE, 1+, 2+, 3+, 4+
Leukocyte Esterase	NEGATIVE, TRACE, 1+, 2+, 3+
Nitrite	NEGATIVE, POSITIVE
pH	5.0, 5.5, 6.0, 6.5, 7.0, 7.5, 8.0, 8.5, >8.5
Protein	NEGATIVE, TRACE, 1+, 2+, 3+, 4+
Specific Gravity	Numeric
Urobilinogen	NORMAL, 1+, 2+, 3+

Qualitative urine parameters are generally reported by a descriptive score, which differs among laboratories. For data analysis purpose, a four-point scale is used. Five-point, six-point, or seven-point scales will be collapsed into a four-point scale first. A value is considered PCST if an upward shift of at least 2 points from the Baseline occurs under investigational treatment. To collapse the results in a five-point scale into a four-point scale, the lowest 2 positive results will be combined as per [Table 13-3](#).

Table 13-3: Conversion of results in a five-point scale into a four-point scale

Original Five-point Scale	Four-point Scale
Negative/None	Negative/None
Trace/Rare/Mild/A Few	Trace/1+/Rare/Mild/A Few
1+	
2+/Mod	2+/Mod

Table 13-3: Conversion of results in a five-point scale into a four-point scale

Original Five-point Scale	Four-point Scale
3+/Sev	3+/Sev

Mod=Moderate, Sev = Severe

The original scale and four-point scale for PCST of each urinalysis parameter is described in **Table 13-4**. Nitrates are not classified into 4-point scales, as there are only 2 values, and pH is not classified into 4-point scales as low and high pH values may be considered as good or bad.

Table 13-4: Urinalysis 4-point scales for PCS criteria

	Four-point Scale			
PARAMETER	Negative	1+	2+	3+
Bilirubin	Negative	1+	2+	3+
Blood	Negative	Trace, 1+	2+	3+
Glucose	Negative	Trace, 1+	2+	3+
Ketones	Negative	Trace, 1+	2+	3+, 4+
Leukocyte Esterase	Negative	Trace, 1+	2+	3+
Protein	Negative	Trace, 1+	2+	3+, 4+
Urobilinogen	Normal	1+	2+	3+

13.1.3 Vital signs and body weight

Table 13-5: Vital signs and body weight PCS criteria

Parameter	Age Range	PCS Criteria
Pulse Rate (beats/minute)	6m - <3y	<90 >150
	3y - <12y	<60 >130
	12y - <17y	<50 >120
	≥17y	<50 and a decrease from Baseline of ≥15 >120 and an increase from Baseline of ≥15
Systolic Blood Pressure (mmHg)	6m - <3y	<70 >120
	3y - <12y	<80

Table 13-5: Vital signs and body weight PCS criteria

Parameter	Age Range	PCS Criteria
		>140
	12y - <17y	<90 >160
	≥17y	≤ 90 and a decrease from Baseline of ≥20 ≥ 180 and an increase from Baseline of ≥20
Diastolic Blood Pressure (mmHg)	6m - <3y	<45 >75
	3y - <12y	<50 >80
	12y - <17y	<50 >105
	≥17y	<50 and a decrease from Baseline of ≥15 >105 and an increase from Baseline of ≥ 15
Respiratory Rate (breaths/minute)	6m - <3y	<20 >45
	3y - <12y	<15 >35
	≥12y	<10 >25
Temperature	>1m	>101.0F (38.3.0C)
Body Weight ^a	1m - <17y	Outside of < 3% or > 97% percentile of the normal body weight based on gender and the age of study participant on date of weight assessment ^b
	≥17y	≥ 10% CFB (an increase or a decrease)

C = Celsius, F = Fahrenheit^b

^a Study participants who turn ≥17y during the EP0132 study, will continue to be assessed in the 1m - <17y category.

^b Assessment will be based on the growth charts from CDC https://www.cdc.gov/growthcharts/clinical_charts.htm

For the assessment of body weight PCS criteria, the participant's age at EP0132 EV will be used to determine the age category as specified in the "Age Range" column of Table 13-5 and

consequently the methodology (ie, percentage change or percentiles) to be used in the assessment of PCS measurements as specified in the “PCS Criteria” column of [Table 13-5](#).

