	Psychiatric and mental status at each applicable visit	Shift from Baseline psychiatric and mental status which are abnormal clinically significant and abnormal not clinically significant
	CFB to each applicable visit in vital signs (blood pressure, pulse rate, body temperature)	Summary statistics of individual visit values and corresponding CFB to each visit
	CFB to each applicable visit in body weight and height	Summary statistics of individual visit values and corresponding CFB to each visit
Secondary objective	Secondary endpoints	
To investigate long-term efficacy of BRV in pediatric study participants with CAE or JAE	Absence seizure freedom within 4 days prior to or during the 1-hour EEG at each applicable visit, up to Month 24	Percentage of study participants free from absence seizures while awake on 1-hour EEG with

Table 3-1: Study endpoints and statistical measures

Objective	Endpoint	Statistical measure(s)
		no concomitant use of AEDs within 4 days prior to or during the 1-hour EEG
	Absence seizure freedom based on diary over the entire Evaluation Period, truncated at Month 24, and by 3-month time intervals up to Month 24	Percentage of study participants free from absence seizures based on diary during Evaluation Period and during each 3-month interval
Secondary objective	Other endpoints	
To investigate long-term efficacy of BRV in pediatric study participants with CAE or JAE	Consecutive absence seizure freedom in 6-month periods based on EEG up to Month 24	Percentage of study participants free from absence seizures in consecutive 6-month periods based on EEG
	Consecutive absence seizure freedom in 6-month periods based on diary up to Month 24	Percentage of study participants free from absence seizures in consecutive 6-month periods based on seizure diary
Tertiary/Exploratory	Other endpoints	
To investigate the long-term effect of BRV on behavior, cognition, and quality of life in pediatric study participants with CAE or JAE	CFB to each applicable visit in the EpiTrack Junior scores (for study participants 6 to <18 years old)	Summary statistics of individual visit values and corresponding CFB to each visit
	CFB to each applicable visit in PedsQL Generic Core scale scores from the study participant self-reports (separate questionnaires for participants age in years: 5 to ≤7, 8 to ≤12, 13 to ≤17 years)	Summary statistics of individual visit values and corresponding CFB to each visit

Table 3-1: Study endpoints and statistical measures

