10.4 Vital signs, physical findings, and other observations related to safety

10.4.1 Vital signs

Systolic blood pressure (SBP), diastolic blood pressure (DBP), pulse rate, temperature, and respiratory rate are assessed at MEV, FEV, YEV, EDV, FV, DTV, and SV. Height and body weight are assessed at MEV, FEV, YEV, FV, and EDV.

Observed values and CFB for each measurement will be summarized at each scheduled visit. Body weight and height will additionally be included in the summary.

The definition of PCS is described in [Section 3.4](#). Vital signs and body weight PCS criteria are located in [Section 13.1.3](#). The number and percentage of study participants with PCST values for each vital sign (ie, PCST low value, PCST high value) will be summarized for each variable individually over all visits (including unscheduled visits) and by visit separately. Percentages in the overall summary will be relative to the number of study participants with at least one assessment on or after the first dose of BRV in EP0132. Percentages in the by visit summary will be relative to the number of study participants with a measurement at the visit. The number of occurrences of each unique PCST type will be tabulated within each scheduled visit.

A study participant data listing of all observed vital sign, body weight and height values will be presented. The listing will contain columns indicating which values met the criteria for PCS.

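### Weight and height change is summarised without age standardisation, and the under-17 weight flag mixes pre-existing with new extreme weights

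*SAP*

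**What the plan says.** SAP Table 3-1 lists "CFB to each applicable visit in body weight and height" among the other endpoints under the primary safety objective. Its statistical measure is "Summary statistics of individual visit values and corresponding CFB to each visit". SAP 10.4.1 describes by-visit summaries of observed values and change for the vital signs, then adds: "Body weight and height will additionally be included in the summary". Change is taken from N01269 Baseline (SAP 3.5). Outputs are split by CAE/JAE and shown for all participants (SAP 3.2, 3.8, 4.4). The optional cuts are dose, exposure duration, 3-month period and COVID-19 period. No age stratum, z-score or growth velocity is planned for weight or height.

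Table 13-5 holds two weight criteria:

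- **Under 17 at the Entry Visit:** "Outside of < 3% or > 97% percentile of the normal body weight" for sex and age, using age on the date of assessment and the CDC growth charts. A footnote keeps this rule after the 17th birthday: "Study participants who turn ≥17y during the EP0132 study, will continue to be assessed in the 1m - <17y category".
- **17 or over:** "≥ 10% CFB (an increase or a decrease".

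Height has no criterion. SAP 3.4 sets the rule for treatment emergence: "Measurements that meet PCS criteria and are treatment-emergent will be considered PCST regardless of whether or not they met the criteria for PCS previously".

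**The concern.** Two features limit what the planned tables can show about growth.

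First, a change in weight or height over two years means different things at age 5, 13 and 24. Averaged over ages within CAE, JAE or overall, it mainly describes who was enrolled and how much they were expected to grow. Because the reference is N01269 Baseline, growth during the core study is included too.

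Second, the under-17 weight flag asks whether a child is at an extreme centile now, not whether the child has moved. Combined with SAP 3.4, a child who was above the 97th percentile before entry and stays there counts as PCST throughout. A child who drops several centile bands but stays inside the limits is never counted. Only those aged 17 or over at entry are judged against their own Baseline weight.

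At stake is whether the summary tables of a long-term paediatric safety study can show a departure from expected growth at all.

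**Working it through.** The plan states no power, effect size or SD for this endpoint, so there is no figure to reproduce. The check illustrates how the planned summaries behave.

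**Inputs from the documents.** Band limits at the 3rd and 97th percentiles (SAP Table 13-5); about 140 participants (SAP 2.4); age range 2 to 26 years (SAP 2.3.1).

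**Assumptions, not in the documents.** Weight-for-age follows a standard normal score in the reference population; 60% to 100% of participants are under 17 at entry; for the raw change only, 50% to 90% are still growing and gain 4 to 12 kg in two years, and the rest do not change.

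**1. Flags with no movement.** Expected share outside the band = 3% + 3% = 6%. If all are under 17: 0.06 × 140 = 8.4 flagged at any visit. If 60% are: 0.06 × 84 = 5.0. None of these children has left their own centile.

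**2. Movement with no flag.** The limits are z = −1.88 and +1.88. The largest fall that stays unflagged is z(start) + 1.88.

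| Starting percentile | z | Unflagged fall, up to |
|---|---|---|
| 50th | 0.00 | 1.88 SD |
| 75th | 0.67 | 2.56 SD |
| 90th | 1.28 | 3.16 SD |

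A fall from the 75th to the 5th percentile is 0.67 − (−1.64) = about 2.3 SD, and the child is not flagged.

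**3. A general downward shift.** If every child moved down 0.5 SD, low flags would rise from 3.0% to 8.4% and high flags would fall from 3.0% to 0.9%. The total would go from 6.0% to 9.2% (8.4 to 12.9 of 140). Low and high values are reported separately under SAP 10.4.1, so the rise in low flags would not be hidden by the total. However, PCST values count only after first dose, and no table of Baseline percentile status is planned. The reader would have no Baseline count to compare with.

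**4. Raw weight change with no departure from expected growth.** Pooled mean = share growing × gain. Lowest: 0.5 × 4 = 2.0 kg. Highest: 0.9 × 12 = 10.8 kg. This range comes from age mix and growth alone.

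**Comparison within the SAP.** Other criteria do use the participant's Baseline: QTcB has a change-from-Baseline limb at every age (Table 13-6), and urinalysis needs an upward shift of at least 2 points (13.1.2). Under-17 pulse and blood pressure use fixed limits, so the SAP follows no single convention.

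**The case against.** The strongest reply is that the plan does what the protocol asks. The endpoint is change from Baseline in weight and height, and that is what is reported. It is classed as other; the primary endpoints are TEAEs and TEAEs leading to discontinuation. Protocol 9.4.1 plans PCST summaries for weight and not for height, so the missing height criterion follows the protocol. The rule in SAP 3.4 is general and openly stated. All of this stands. It means that the change is an improvement to the summaries and does not repair an unmet endpoint.

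Three stronger readings are tempting, and the documents do not support them.

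- **A reader might infer that weight is judged with no allowance for growth.** The under-17 flag is referenced to sex and to age at assessment, so its cut-off moves with normal growth. What it lacks is the child's own starting point.
- **A reader might infer that slowed growth or weight loss could not be seen, so that part of the primary objective goes unanswered.** SAP 10.4.1 lists every observed weight and height, with PCS columns. Protocol Appendix 3 makes clinically significant vital-sign abnormalities adverse events, including worsening from Baseline, and protocol 8.1.5 counts body weight among the vital signs. A large fall can be found in the listings and, if judged clinically significant, enters the TEAE analysis. It is the planned summary tables that miss it.
- **A reader might infer that standardising would isolate a drug effect.** The study has one arm. Z-scores remove expected growth and nothing more.

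**Conclusion.** The point holds for the planned summaries. Mean change in weight and height is not standardised for age, and the under-17 weight table combines children already outside the band with children newly outside it, while missing large shifts inside the band.

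The size is an illustration: about 6% of under-17s flagged at any visit with no change of centile, or 5.0 to 8.4 participants as the under-17 share runs from 60% to 100% of 140. It rests on the sample matching the reference weight distribution. The 2.0 to 10.8 kg range rests on assumed shares and gains.

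The documents give no SD for height or weight change, so nothing here shows how large a mean growth effect would be detectable. Setting the wide range of individual growth against a small mean slowing would not show it either. The primary endpoints are unaffected.

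**What to change.** 1. In SAP 10.4.1 and Table 3-1, for participants within the age range of the cited CDC charts, add descriptive summaries of weight-for-age and height-for-age z-score and of change in z-score from N01269 Baseline. Keep the raw summaries.
2. For the under-17 weight PCST table (SAP 10.4.1, Table 13-5), report low and high flags separately, each split into already outside the band at N01269 Baseline and newly outside.
3. Do not add a flag for a z-score shift unless the sponsor states its limit in advance.
4. Say in the SAP that these summaries remove expected growth and do not establish a drug effect.

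The cost is one derivation and a few more table rows. Weight and height are measured at every Evaluation Period clinic visit after entry except unscheduled visits (protocol 8.1.2), age in months and years is collected at each scheduled visit (SAP 4.1.4.2), and sex comes from the N01269 database (SAP 3.3.6). No new data are required.
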